4.2 Rationale

4.2.1 Rationale for the Trial and Selected Subject Population

The current paradigm for treatment of nr-axSpA with TNF inhibitors is to maintain treatment on a chronic basis. Data regarding alternate treatment paradigms with TNF inhibitors for the long-term management of nr-axSpA are not available. An example of an alternate treatment paradigm is to adjust the dosing regimen, guided by clinical symptoms and signs. The purpose of this trial is to evaluate the effects of golimumab treatment withdrawal, compared with continued golimumab treatment (either QM or Q2M), during approximately up to 12 months. Efficacy and safety results of this trial will provide investigators and clinicians with important information regarding dose optimization of golimumab for treatment of nr-axSpA, especially for subjects who show a good response to golimumab within 4 months and then have inactive disease status after both 7 and 10 months of open-label treatment in Period 1.

The subject population in this trial is aligned with the population for which golimumab is approved for use in the European Union (EU). Namely, subjects to be enrolled must have active nr-axSpA with objective signs of inflammation who are either intolerant of, or have

demonstrated a lack of response to, NSAIDs. Subjects are adults (i.e., age ≥ 18 years) who are ≤ 45 years of age; excluding older adults is consistent with guidance from ASAS classification criteria for axial spondyloarthritis (SpA).

4.2.2 Rationale for Dose Selection/Regimen

The dose and regimen of golimumab selected for open-label treatment in this study is consistent with its approved use:

- Golimumab 50 mg is given SC monthly.
- For subjects with a body weight more than 100 kg who do not achieve an adequate clinical response after up to 3 doses, increasing the dose of golimumab to 100 mg SC monthly may be considered (as described in Section 5.2.1.2).

4.2.3 Rationale for Endpoints

4.2.3.1 Efficacy Endpoints

Inactive disease status and a disease “flare” in this trial are defined using the ASDAS. The ASDAS was developed by ASAS as an index for disease activity measurement in axial SpA that includes subjective measures (rated by the subject) and objective measure (CRP) to create a well-balanced index [3]. This score combines 5 disease activity variables that have only partial overlap, resulting in one single score with better validity, enhanced discriminative capacity, and improved sensitivity to change as compared with single-item variables. Cutoffs to identify “disease activity states” and “response criteria” using the ASDAS were first identified in 2011 [4]. This trial will use the cutoffs defined by ASAS:

- Level of ASDAS to identify subjects with inactive disease: ASDAS < 1.3 ;
- Level of ASDAS to identify subjects with a “flare”: ASDAS ≥ 2.1 (which defines high disease activity) and/or a change in ASDAS by ≥ 1.1 (which is considered a clinically important change).

The BASDAI score, which combines 6 questions that are self-assessed by subjects, is used to define a clinical response in this trial, both to open-label treatment with golimumab and to re-treatment with open-label golimumab after a “flare”. Clinical response is defined as a BASDAI score improvement by ≥ 2 (on a 0 to 10 scale) and/or score improvement by $\geq 50\%$. This definition of a “responder” is from the ASAS recommendations for use of TNF inhibitors in subjects with Axial SpA [2]. To assess the response to open-label golimumab, the response is compared with the BASDAI score at Month 0; to assess the response to re-treatment, the response is compared with the mean of the 2 BASDAI scores obtained when the “flare” was diagnosed.

To characterize the symptoms and signs of nr-axSpA in subjects treated with golimumab or withdrawn from golimumab, other secondary endpoints will be assessed in this trial. These include ASAS20, ASAS40, BASDAI50, and ASAS Partial Remission. All of these endpoints have been studied in many previous studies of axial SpA. Of note, in the GO-AHEAD

(P07642) trial in subjects with nr-axSpA, golimumab was shown to be superior to placebo for each of these endpoints [1].

4.2.3.2 Safety Endpoints

The analysis of safety results will follow a tiered approach; the tiers differ with respect to the analyses that will be performed (as described in Section 8.6.2). Adverse events (AEs) refer to both clinical and laboratory AEs. The safety tiers are defined as follows:

Tier 1: Serious Infections, serious opportunistic infections, active tuberculosis, malignancies, and serious systemic hypersensitivity (including anaphylactic reaction) are prespecified as “Tier-1” events (for analysis of differences between treatments) in double-blind Period 2; and as “Select safety endpoints of interest” (for display as listings) in open-label Period 1.

Any AEs (specific terms, as well as system organ class terms) that are not pre-specified as Tier-1 endpoints will be classified as belonging to "Tier 2" or "Tier 3", based on the numbers of events observed.

Tier 2: Treatment-emergent AEs that occur with at least 4 events in at least one treatment group)

Tier 3: Treatment-emergent AEs that occur with inadequate frequency to qualify as Tier-2 AEs, predefined limits of change for laboratory test results, routine safety measures including vital signs.

4.2.3.3 Planned Exploratory Biomarker Research

Understanding genetic determinants of drug response is an important endeavor during medical research. This research will evaluate whether genetic variation within a clinical trial population correlates with response to the treatment(s) under evaluation. If genetic variation is found to predict efficacy or AEs, the data might inform optimal use of therapies in the patient population. This research contributes to understanding genetic determinants of efficacy and safety associated with treatments in this study.

4.2.3.4 Future Biomedical Research

The Sponsor will conduct Future Biomedical Research on DNA specimens collected for future biomedical research during this clinical trial.

Such research is for biomarker testing to address emergent questions not described elsewhere in the protocol (as part of the main trial) and will only be conducted on specimens from appropriately consented subjects. The objective of collecting specimens for Future Biomedical Research is to explore and identify biomarkers that inform the scientific understanding of diseases and/or their therapeutic treatments. The overarching goal is to use such information to develop safer, more effective drugs/vaccines, and/or to ensure that subjects receive the correct dose of the correct drug/vaccine at the correct time. The details of this Future Biomedical Research sub-trial are presented in Section 12.2 - Collection and Management of Specimens for Future Biomedical Research. Additional informational

material for institutional review boards/ethics committees (IRBs/ERCs) and investigational site staff is provided in Section 12.3.

4.3 Benefit/Risk

Golimumab has been shown to be effective and generally safe and well-tolerated in subjects for the treatment of nr-axSpA, and it is currently approved for use in this disease. The risks of golimumab include serious infections (including opportunistic infections and tuberculosis), congestive heart failure, lymphoma (and other malignancies), infusion-related reactions, and other risks as detailed in the current product labeling.

In this trial, subjects who have insufficient benefit from the approved regimen of golimumab, after approximately 4 months of open-label treatment, are to be discontinued from the study, so they can seek alternative therapy. Subjects are also discontinued from the study if they have not attained inactive disease status after either 7 or 10 months of open-label treatment. Subjects who attain inactive disease after both 7 and 10 months of open-label golimumab can then be randomly withdrawn from treatment or continued on treatment using a full regimen (golimumab QM) or a reduced regimen (golimumab Q2M). All randomized subjects are monitored for the risk of a worsening in their disease: subjects are closely followed (using self-ratings of their disease, collected twice monthly) and closely observed (at clinic visits every 2 months). The risk of this investigational treatment paradigm is that subjects may experience worsening of their symptoms upon withdrawal of golimumab and may not respond as effectively to golimumab when it is reinitiated to treat a “flare”.

The benefits of this investigational treatment paradigm are that subjects will receive golimumab at the approved dose and regimen for the first 10 months of the trial and can reasonably expect to experience adequate control of their disease. The trial may demonstrate that control of symptoms is adequate following withdrawal of golimumab for a period of time and that continuous use (whether using a full regimen or a reduced regimen) is not necessary in all subjects. The benefit of this paradigm will be less exposure to golimumab and potentially the reduction in established risks associated with use of a TNF-inhibitor, such as serious infections and malignancies.

Additional details regarding specific benefits and risks for subjects participating in this clinical trial may be found in the accompanying Investigators Brochure (IB) and ICF documents.

5.0 METHODOLOGY

5.1 Entry Criteria

5.1.1 Diagnosis/Condition for Entry into the Trial

Adult subjects with active nr-AxSpA, who have objective signs of inflammation and intolerance or inadequate response to NSAIDs, will be enrolled in this trial.

5.1.2 Subject Inclusion Criteria

In order to be eligible for participation in this trial, the subject must:

1. Be male or female and must be ≥ 18 to ≤ 45 years of age.
2. Be able to provide written informed consent for the trial and may also provide consent for Future Biomedical Research. However, the subject may participate in the trial without participating in Future Biomedical Research.
3. Meet one of the following categories:
 - a) The subject is a male who is not of reproductive potential, defined as a male who has azoospermia (whether due to having had a vasectomy or due to an underlying medical condition).
 - b) The subject is a female who is not of reproductive potential, defined as a female who either: (1) Postmenopausal is defined as at least 12 consecutive months without a spontaneous menstrual period; (2) has had a hysterectomy and/or bilateral oophorectomy, bilateral salpingectomy, or bilateral tubal ligation/occlusion at least 6 weeks prior to screening; OR (3) has a congenital or acquired condition that prevents childbearing.
 - c) The subject is a female or a male who is of reproductive potential and agrees to avoid becoming pregnant or impregnating a partner while receiving trial medication or within 6 months after the last dose of trial medication by complying with one of the following: (1) practice abstinence[†] from heterosexual activity OR (2) use (or have their partner use) acceptable contraception during heterosexual activity.

Acceptable methods of contraception are[†]:

- intrauterine device (IUD)
- vasectomy of a female subject's male partner
- contraceptive rod implanted into the skin
- barrier method (includes diaphragm, cervical cap, and male or female condom) with spermicidal gel or foam
- hormonal contraceptive: oral contraceptive pill (estrogen/progestin pill or progestin-only pill), contraceptive skin patch, vaginal contraceptive ring, or subcutaneous contraceptive injection

[†]Abstinence (relative to heterosexual activity) can be used as the sole method of contraception if it is consistently employed as the subject's preferred and usual lifestyle and if considered acceptable by local regulatory agencies and ERCs/IRBs. Periodic abstinence (e.g., calendar, ovulation, sympto-thermal, post-ovulation methods, etc.) and withdrawal are not acceptable methods of contraception.

‡If a contraceptive method listed above is restricted by local regulations/guidelines, then it does not qualify as an acceptable method of contraception for subjects participating at sites in this country/region.

4. Have chronic back pain of ≥ 3 months duration by history.
5. Have a physician's diagnosis of active nr-axSpA with disease duration ≤ 5 years.

Note: Disease duration is defined as the length of time since onset of symptoms

6. Meet either criterion "a" or "b" as adopted from ASAS classification criteria:
 - a. Active inflammation on MRI highly suggestive of sacroiliitis associated with spondyloarthropathy and 1 or more of the following spondyloarthritis characteristics:
 - Inflammatory back pain, defined as having at least 4 out of the 5 following parameters:
 - age at onset <40 years;
 - insidious onset;
 - improvement with exercise;
 - no improvement with rest;
 - pain at night (with improvement upon getting up);
 - Arthritis diagnosed by a physician;
 - Enthesitis (heel) diagnosed by a physician: Spontaneous pain or tenderness at examination of the site of the insertion of the Achilles tendon or plantar fascia at the calcaneus;
 - Dactylitis diagnosed by a physician;
 - Psoriasis diagnosed by a physician;
 - History of inflammatory bowel disease (IBD) diagnosed by a physician;
 - History of uveitis confirmed by an ophthalmologist;
 - Good response to NSAIDs: (Good response is defined as "24-48h after a full dose of NSAID the back pain is not present anymore or is much better");
 - Family history for SpA: Presence in first-degree (mother, father, sisters, brothers, children) or second-degree (maternal and paternal grandparents, aunts, uncles, nieces and nephews) relatives of any of the following: (1) AS; (2) psoriasis; (3) acute uveitis; (4) reactive arthritis; (5) IBD;
 - Elevated CRP (based on values obtained through a central laboratory);
 - Human leukocyte antigen B27 (HLA-B27)+ gene

OR

b. HLA-B27+ gene and 2 or more of the following spondyloarthritis characteristics:

- Inflammatory back pain, defined as having at least 4 out of the 5 following parameters:
 - age at onset <40 years;
 - insidious onset;
 - improvement with exercise;
 - no improvement with rest;
 - pain at night (with improvement upon getting up);

- Arthritis diagnosed by a physician;
- Enthesitis (heel) diagnosed by a physician:

Spontaneous pain or tenderness at examination of the site of the insertion of the Achilles tendon or plantar fascia at the calcaneus;

- Dactylitis;
- Psoriasis diagnosed by a physician;
- History of inflammatory bowel disease (IBD) diagnosed by a physician
- History of uveitis confirmed by an ophthalmologist;
- Good response to NSAIDs;

Note: Good response is defined as “24-48h after a full dose of NSAID the back pain is not present anymore or is much better”

- Family history for SpA:

Presence in first-degree (mother, father, sisters, brothers, children) or second-degree (maternal and paternal grandparents, aunts, uncles, nieces and nephews) relatives of any of the following: (1) AS; (2) psoriasis; (3) acute uveitis; (4) reactive arthritis; (5) IBD;

- Elevated CRP (based on values obtained through a central laboratory).

7. Have elevated CRP at the Screening visit or evidence of active inflammation in the SI joints on MRI.

Note: Elevated CRP is defined as a value that is >6.0 mg/L; a maximum of 40% of enrolled subjects may have normal CRP at the Screening visit. All MRIs must undergo central reading to determine study eligibility.

8. Have ASDAS ≥ 2.1 at the Screening visit.

9. Show high disease activity at Screening and Baseline of both a Total Back Pain score of ≥ 4 and a BASDAI score of ≥ 4 (each on a NRS of 0 to 10).

10. Have an acceptable history of use of NSAIDs: either an inadequate response, as assessed by the investigator, with maximal recommended daily doses of at least 2 NSAIDs; or must be unable to receive maximal NSAID therapy because of intolerance, toxicity, or contraindications to NSAIDs. (Note: It is possible that a subject had a good response initially to NSAIDs but subsequently had inadequate response or developed intolerance to NSAIDs therapy).
11. Have acceptable current use of NSAIDs at Screening:
 - If currently using an NSAID, must be on a stable daily dose for at least 14 days prior to Screening
Note: Such use of NSAIDs is allowed and will be monitored during the study.
 - If not currently using an NSAID, short-term use is allowed (up to 1 week) during Period 1 and is allowed as needed during Period 2.
Note: Such use of NSAIDs will be monitored during the study.
12. Tuberculosis Assessment (see also Section 7.1.3.3):
 - a. Have no history of untreated latent or active tuberculosis (TB) prior to screening. An exception is made for subjects who have a history of latent TB and are currently receiving treatment for latent TB, will initiate treatment for latent TB prior to first administration of study agent, or have documentation of having completed appropriate treatment for latent TB within 5 years prior to the first dose of administration of study agent. It is the responsibility of the investigator to verify the adequacy of previous anti-tuberculous treatment and provide appropriate documentation.
 - b. Have no signs or symptoms suggestive of active TB upon medical history and/or physical examination.
 - c. Have had no recent close contact with a person with active TB or, if there has been such contact, will be referred to a physician specializing in TB to undergo additional evaluations and receive appropriate treatment for latent TB prior to the first administration of study agent.

- d. Within 6 weeks prior to the first administration of study agent, have a negative QuantiFERON®-TB Gold test result, or have a newly identified positive QuantiFERON®-TB Gold test result in which active TB has been ruled out and for which appropriate treatment for latent TB has been initiated prior to the first administration of study agent. Within 6 weeks prior to the first administration of study agent, a negative tuberculin skin test, or a newly identified positive tuberculin skin test in which active TB has been ruled out and for which appropriate treatment for latent TB has been initiated prior to the first administration of study agent, is additionally required if the QuantiFERON®-TB Gold test is not approved/registered in that country or the tuberculin skin test is mandated by local health authorities.
- If, based on the investigator's judgment of a subject's high risk of latent TB infection, the QuantiFERON®-TB Gold test and the tuberculin skin test are both performed, and if either is positive, and if active TB has been ruled out, then appropriate treatment for latent TB must be initiated prior to the first administration of study agent.
 - Subjects with persistently indeterminate QuantiFERON®-TB Gold test results may be enrolled without treatment for latent TB, if active TB is ruled out, their chest radiograph shows no abnormality suggestive of TB (active or old, inactive TB), and the subject has no additional risk factors for TB as determined by the investigator. This determination must be promptly reported to the sponsor's medical monitor and recorded in the subject's source documents and initialed by the investigator.
 - The QuantiFERON®-TB Gold test and the tuberculin skin test are not required at screening for subjects with a history of latent TB and ongoing treatment for latent TB or documentation of having completed adequate treatment as described above; subjects with documentation of having completed adequate treatment as described above **are not** required to initiate additional treatment for latent TB.
- e. Have a chest radiograph (both posterior-anterior and lateral views) within 3 months prior to the first administration of study agent and read by a qualified radiologist, with no evidence of current, active TB or old, inactive TB.
13. Be judged to be medically stable, other than nr-axSpA, based on medical history, physical examination, and routine laboratory tests.

14. Undergo screening for hepatitis B virus (HBV), which at a minimum includes testing for HBV surface antigen (HBsAg), HBV surface antibody (anti-HBs), and HBV core antibody (anti-HBc total), and demonstrate to be eligible based on the following results:

Action	Hepatitis B Surface Antigen(HBsAg)	Hepatitis B Surface Antibody(anti-HBs)	Hepatitis B Core Antibody(anti-HBc Total)
Exclude	+	- or +	- or +
Include	-	+	+
Include	-	+	-
Include	-	-	-
Require Hepatitis B viral DNA (HBV DNA) testing*	-	-	+
* If HBV DNA is detectable or there is evidence of chronic liver disease, exclude from clinical trial. If the HBV DNA test is negative, the subject is eligible for this trial. In the event the HBV DNA test cannot be performed, the subject is not eligible for this trial.			

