f. Also contains contact information for the emergency unblinding call center so that a health care provider can obtain information about trial medication in emergency situations when the investigator is not available.

g. Sites to call IVRS to register the subject at V1; to assign allocation number at V2; to assign trial medications from V2 to V23; to update subject disposition at DC visit.

h. After proper training, subjects may self-inject trial medication monthly ± 5 days, if their physician determines it is appropriate and with medical follow-up as necessary.

i. The first physical exam (PE) (performed at Screening) will be a complete PE, including a full skin examination and excluding genital and urinary. Subsequent PEs would include a full skin assessment and would be directed to evaluate signs and symptoms of potential AEs.

j. Height (with the shoes removed) and weight (in street clothing with jacket/coat and shoes removed) should be collected at the screening visit only.

k. Subjects who have chest x-ray performed within 3 months prior to Screening with no clinically significant findings do not need to have chest x-ray repeated at Screening.

l. For subjects who have a SI joint x-ray performed within 6 months prior to Screening, the site can send the x-ray for central reading. If these x-rays are evaluable by central reading, then these subjects do not need to have a SI joint x-ray repeated at Screening.

m. Screening MRI should be performed for subjects only if the CRP value is normal and subject is otherwise deemed to be eligible for the study. For subjects who have MRI performed within 6 months prior to Screening, the site can send MRI films for central reading. If these films are evaluable by central reading, then these subjects with clinical evidence of inflammation do not need to have a MRI repeated at Screening.

n. Each subject must show high disease activity at Screening and Baseline as measured by Total Back Pain score ≥ 4 and a BASDAI score ≥ 4 on 0 to 10 NRS.

o. If local law requires more frequent pregnancy testing, the site will perform the assessments as per local requirement.

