7.1.2.3 Chest X-ray (CXR)

For this protocol, a chest x-ray is mandatory to assess the tuberculosis (TB) screening eligibility criterion. Subjects should have a chest x-ray within 3 months prior to the screening visit with no evidence of current active TB or old inactive TB. If a negative chest x-ray is not available, then the subject must have a chest x-ray performed during screening showing no evidence of active or inactive TB.

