7.1.3.3 Tuberculosis (TB) Screening

For this protocol, a chest x-ray AND a QuantiFERON[®]-TB Gold test are mandatory, regardless of local guideline preferences. In addition, all subjects must undergo all additional applicable tests for TB (such as tuberculin skin test) and latent TB screening in accordance with local guidelines and protocol requirements.

Subjects who have negative diagnostic TB test results are considered eligible for the trial. A subject with a positive result for active TB should not be included in the current trial. The TB testing should be completed during the Screening visit and the results must be reviewed to assess subject eligibility prior to the Baseline visit. Tests include, but are not limited to posterior-anterior and lateral chest x-rays (unless a chest x-ray has been performed within 3 months prior to first treatment administration) and QuantiFERON[®]-TB Gold test (unless performed within 6 weeks prior to the first treatment administration), and tuberculin skin test.

Within 6 weeks prior to first administration of trial medication, subjects should have:

- negative diagnostic TB test results (defined as a negative QuantiFERON-TB Gold test [and a negative tuberculin skin test, but only if tuberculin skin test is needed]), OR
- a newly identified positive TB test result (defined as positive QuantiFERON-TB Gold test [and/or a positive tuberculin skin test, but only if tuberculin skin test is needed]) during Screening for which active TB has been ruled out and for which appropriate treatment for latent TB has been initiated prior to the first administration of trial medication. The duration of the treatment before the first administration should be in accord with local guidelines, if any.

Investigators have the option to use both the QuantiFERON-TB Gold test and the tuberculin skin test to screen for latent TB if they believe, based on their judgment, that the use of both tests is clinically indicated in order to evaluate a subject who has high risk of having latent TB. Local guidelines specifically directed to high risk and/or immunocompromised subjects should be used for screening and interpreting positive test results for TB.

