7.1.5.1 Screening and Baseline Eligibility (Visit 1 and Visit 2)

All screening procedures (including MRI) required to assess subjects' eligibility for the trial should be completed within the 2 months (60 days) prior to administration of the first dose of open-label golimumab at Visit 2. IVRS/IWRS should be used beginning with the Screening visit and ending with completion/discontinuation visit.

Subjects in this study may be rescreened once prior to receiving open-label golimumab, with prior approval by the Sponsor trial physician. If a subject is rescreened, the same screening number must be used.

When it is confirmed at Baseline (Visit 2 or “Month 0”) that a subject is eligible to enter Period 1 (to receive open-label golimumab), the subject should be assigned an allocation number using the IVRS/IWRS. Refer to the IVRS/IWRS user manual for additional details.

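### The 3-month limit on the TB chest film runs from first dose in two places and from Screening in two others, so a film up to about 151 days old at first dose can pass one rule and fail the other

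*Combined protocol and SAP*

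**What the plan says.** Four places in the current protocol text set an age limit for the same chest film.

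- **Section 5.1.2, criterion 12e**, counts from first dose. The subject must "Have a chest radiograph (both posterior-anterior and lateral views) within 3 months prior to the first administration of study agent".
- **Section 7.1.3.3 (TB screening)** also counts from first dose. New films are among the tests listed "unless a chest x-ray has been performed within 3 months prior to first treatment administration".
- **Section 7.1.2.3 (chest x-ray)** counts from Screening: "Subjects should have a chest x-ray within 3 months prior to the screening visit". It asks for a new film only in one case: "If a negative chest x-ray is not available, then the subject must have a chest x-ray performed during screening".
- **Section 6.1, flow-chart footnote k**, also counts from Screening. It says that subjects with a "chest x-ray performed within 3 months prior to Screening with no clinically significant findings do not need to have chest x-ray repeated at Screening".

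Section 7.1.2.3 is written for the same purpose as 12e. It states that "a chest x-ray is mandatory to assess the tuberculosis (TB) screening eligibility criterion".

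The gap between the two reference points is set by Section 7.1.5.1: screening procedures "should be completed within the 2 months (60 days) prior to administration of the first dose of open-label golimumab at Visit 2". Section 2.1 gives the same 60-day ceiling.

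**The concern.** If Screening and first dose fell on the same day, the two reference points would agree. They can be up to 60 days apart, so a film that is recent enough at Visit 1 may be too old at Visit 2. For such a film, Section 7.1.2.3 and footnote k call for nothing further, while 12e and Section 7.1.3.3 say it no longer counts. No text says which prevails.

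The film is a tuberculosis check before a TNF inhibitor is started, and Section 4.3 lists tuberculosis among golimumab's risks. It carries most weight where the blood test tells least. Under criterion 12d, subjects with persistently indeterminate QuantiFERON results may enrol without latent-TB treatment if, among other conditions, "their chest radiograph shows no abnormality suggestive of TB (active or old, inactive TB". Subjects with latent TB under treatment, or with documented adequate treatment, are excused both the QuantiFERON and the skin test.

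Two things are at stake: how current that safety check is, and avoidable eligibility deviations at sites that follow the procedural text as written.

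**Working it through.** The documents state no maximum film age, so there is no plan figure to reproduce. The check is date arithmetic.

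**Inputs**

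- Film window: 3 months, in all four places. I take this as 91 days and vary it below.
- Longest interval from Screening to first dose: 60 days (Sections 2.1 and 7.1.5.1).
- QuantiFERON window: 6 weeks = 42 days before first dose (criterion 12d and Section 7.1.3.3, which agree).

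**Formulas**

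Let d be the days from film to Visit 1, and s the days from Visit 1 to first dose. Film age at first dose is d + s.

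- Section 7.1.2.3 and footnote k accept d ≤ 91.
- Criterion 12e and Section 7.1.3.3 require d + s ≤ 91.
- The rules conflict when 91 − s < d ≤ 91, a band s days wide.

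**Worked example**

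A normal film is taken 80 days before Visit 1 and dosing is 30 days after it. Since 80 ≤ 91, the Screening rule accepts the film. Its age at dosing is 80 + 30 = 110 days, which is 110 − 91 = 19 days too old under 12e.

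**How wide the conflict is**

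| Days from Visit 1 to first dose (s) | Films in conflict (days before Visit 1) | Oldest accepted film at first dose | Days over the 12e limit |
|---|---|---|---|
| 14 | 78 to 91 | 91 + 14 = 105 | 14 |
| 30 | 62 to 91 | 91 + 30 = 121 | 30 |
| 42 | 50 to 91 | 91 + 42 = 133 | 42 |
| 60 | 32 to 91 | 91 + 60 = 151 | 60 |

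**Sensitivity to the length of 3 months**

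With 90 or 92 days, the maximum is 150 or 152. Using calendar months, over every first-dose date in 2017 and 2018, the maximum age under the Screening rule is 149 to 152 days (mean 151.3). The 12e limit is 89 to 92 days, and the gap is 57 to 62 days.

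**Which subjects can reach the maximum**

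The flow chart places the QuantiFERON test at Visit 1. A subject tested only then must be dosed within 42 days, so the maximum is the 133 days in the s = 42 row. Reaching 151 days needs a later or repeated QuantiFERON test, or a subject excused from it.

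**The case against.** The strongest reply is that the protocol's structure already settles the matter. Criterion 12e is a condition of entry. Section 7.1.1.2 requires all Section 5.1 criteria to be reviewed, and the flow chart schedules that review at Visit 2 as well as Visit 1. Criterion 12 refers the reader to Section 7.1.3.3, which agrees with it. Section 7.1.2.3 says only what subjects should have, and footnote k waives a repeat at Screening without saying that the film meets 12e. A site can always comply with everything by applying the stricter rule, and nothing bars a new film.

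Much of this stands. A careful Visit 2 review would catch a 110-day-old film. It does not remove the conflict, because Section 7.1.2.3 is the instruction for carrying out this TB eligibility check and gives a different limit. It asks for a new film only when no negative one is available, and the flow chart schedules a film only at Visit 1. A site holding a clear film at Visit 1 has been told that nothing more is needed.

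The second reply is that 151 days is a corner case. That is fair: it needs a film at the edge of the window and a full 60-day screening, and for a subject tested with QuantiFERON only at Visit 1 the limit is 133 days. The higher figure remains reachable, and among those who can reach it are subjects with treated latent TB, who have no QuantiFERON clock.

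The third reply is that the film is one safeguard among several. Symptoms and TB contacts are checked in everyone, and the adequacy of earlier treatment must be verified. Untreated entry with an indeterminate result also requires that active TB be ruled out, that there be no additional risk factors, and that the determination be reported to the medical monitor. This limits the harm but gives no reason to keep two limits.

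**Conclusion.** The concern holds. Two current texts count the chest film's 3 months from first dose, two count from Screening, and nothing reconciles them. The largest discrepancy is about 60 days: a film up to about 151 days old at first dose against a limit of about 91. For subjects whose only QuantiFERON test is at Visit 1, the corresponding figures are 133 days and 42 days over.

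These figures assume that 3 months is 91 days and that screening can run its full 60 days. The conflict itself needs neither: any interval between Visit 1 and first dose leaves a band of films that one rule accepts and the other rejects. Films taken during Screening are unaffected. How many subjects fall in the band cannot be derived, because the documents give no film dates or screening intervals.

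This is a matter of eligibility and TB safety. Power, type I error and the Period 2 treatment comparison do not change. It should be corrected.

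**What to change.** Count from first dose everywhere, as criterion 12e and Section 7.1.3.3 already do.

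- **Section 7.1.2.3:** change the reference point for the 3 months from the screening visit to the first administration of study agent.
- **Section 6.1, footnote k:** change the reference point from Screening to the planned first dose at Visit 2, and add that otherwise the film is repeated during Screening.
- **Optional, Section 7.1.3.3:** say that TB testing is completed during the screening period, not the screening visit.

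The cost is two wording changes in an amendment, plus the optional third. Subjects whose earlier film passes 3 months before Visit 2 need a repeat two-view chest x-ray, with its small radiation dose. Criterion 12e already requires that film, so the change adds no new requirement.
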